Study Protocol

Official Title

ESKPSY: Esketamine in Real-World Settings – Clinical Outcomes, Predictors of Response, Life Functioning and Biological Pathways

NCT Number

To be assigned by ClinicalTrials.gov

Date

August 2025

1. Background and Rationale

Treatment-resistant depression (TRD) represents a significant clinical challenge, with limited effective pharmacological options. Esketamine, a non-competitive NMDA receptor antagonist, has shown promise in improving symptoms in TRD patients, with a rapid onset of antidepressant action. However, not all patients respond equally, and predictors of treatment response remain unclear.

Emerging literature suggests that clinical, biological (including genetic polymorphisms and neuroimaging), and psychosocial variables may contribute to esketamine response variability. Building on studies such as Guglielmo et al. (2023), which explored the role of temperament and cumulative resistance, this study aims to deepen understanding of real-world predictors of esketamine effectiveness and safety.

2. Study Objectives

Primary Objective:

• To identify predictive factors (clinical, biological, psychophysical, and functional) of clinical response to esketamine in patients with treatment-resistant depression.

Secondary Objectives:

- To evaluate the effectiveness and safety of esketamine in a real-world clinical setting.
- To explore changes in psychosocial and occupational functioning over time.
- To investigate biological pathways associated with treatment response, including genetic polymorphisms (SNPs), neuroimaging data, and psychophysical tasks (e.g., temporal bisection).

3. Study Design

• **Study Type:** Observational

- **Design:** Prospective, longitudinal, single-arm (case-only)
- **Duration:** From enrollment to 12 months of treatment
- Setting: Real-world clinical practice across outpatient psychiatric centers in Italy
- Estimated Enrollment: 100

4. Population

Inclusion Criteria:

- Adults (≥18 years) diagnosed with Major Depressive Disorder (MDD), meeting criteria for treatment-resistant depression (failure of ≥2 antidepressants)
- Eligible for esketamine treatment as per national guidelines
- Ability to provide informed consent

Exclusion Criteria:

- Current diagnosis of psychotic disorder
- Contraindications to esketamine
- Substance use disorder (moderate to severe) in the past 6 months
- Significant cognitive impairment or neurological conditions

5. Intervention (Observed Treatment)

- Esketamine nasal spray, administered in accordance with the approved product label:
 - O Dosage ranging from 28 mg to 84 mg per week
 - o **Twice-weekly administration during the first month**, followed by weekly maintenance

6. Outcome Measures

Primary Outcome:

• Identification of **predictive factors of clinical response** to esketamine, measured using standard clinical scales (e.g., MADRS) at baseline and regular follow-ups.

Secondary Outcomes:

- Changes in depressive symptoms over time
- Changes in social and occupational functioning
- Safety and tolerability (adverse events monitoring)
- Associations between response and:
 - o Genetic polymorphisms (SNPs)
 - o Neuroimaging features (e.g., structural and functional MRI)
 - Psychophysical performance (e.g., temporal bisection tasks)

7. Data Collection and Timepoints

- **Baseline**: Clinical, demographic, neuroimaging, genetic, psychophysical assessments
- **Follow-ups**: At 1, 3, 6 and 12 months
 - Clinical scales
 - Functional assessments
 - Safety monitoring

8. Statistical Analysis Plan (SAP)

- **Descriptive statistics** for demographic and clinical variables
- Logistic regression and machine learning models to identify predictive factors of response
- Longitudinal analysis (mixed-effects models) for symptom trajectories and functioning
- Correction for multiple comparisons where appropriate (e.g., false discovery rate)

9. Ethics and Dissemination

- The study will be conducted in accordance with the Declaration of Helsinki.
- Ethical approval has been or will be obtained from local institutional review boards.
- Results will be submitted for publication in peer-reviewed journals and presented at international psychiatric conferences.

10. Funding and Conflicts of Interest

• The investigators declare no conflicts of interest unless otherwise stated.

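### Does listing SNP, neuroimaging and psychophysical predictors under both the primary and the secondary objectives leave the primary analysis open to relabelling?

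*Protocol*

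**What the plan says.** The primary objective in Protocol Section 2 is "To identify predictive factors (clinical, biological, psychophysical, and functional) of clinical response to esketamine". Section 1 shows what the protocol means by the second of these domains: "biological (including genetic polymorphisms and neuroimaging". The third secondary objective reads "To investigate biological pathways associated with treatment response, including genetic polymorphisms (SNPs), neuroimaging data, and psychophysical tasks".

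Section 6 has the same layout. The primary outcome is the set of factors predictive of response, with no domain excluded. The secondary outcomes include, under "Associations between response and", SNPs, "Neuroimaging features (e.g., structural and functional MRI" and "Psychophysical performance (e.g., temporal bisection tasks".

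Section 7 collects all of these at baseline: "Clinical, demographic, neuroimaging, genetic, psychophysical assessments". Section 8 gives one analysis line for predictors, "Logistic regression and machine learning models to identify predictive factors of response". It adds a multiplicity correction to be used where appropriate, with FDR as an example. No predictor list, family of tests or error level is given. Section 3 sets enrolment at 100 in an observational, single-arm design.

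**The concern.** The same patients, response and predictors appear in two tiers, and no sentence ranks them. Read strictly, an investigator could call a SNP or MRI result primary if it came out well and secondary if it did not. Clinical predictors could be corrected as a family of their own or pooled with the biological tests, whichever suited. The identification of predictors is the study's main question and 100 patients is a small sample, so a finding near the threshold might stand or fall on a choice made after the data were seen.

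**Working it through.** **The texts side by side.**

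| Tier | Domains named | Task |
|---|---|---|
| Primary (Sections 2 and 6) | clinical, biological, psychophysical, functional (Section 2); no domain excluded (Section 6) | identify predictors of response |
| Secondary (Sections 2 and 6) | SNPs, neuroimaging, psychophysical tasks | pathways and associations with response |

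The overlap is exact for SNPs, neuroimaging and psychophysical tasks. The verbs differ: the primary tier predicts, the secondary tier describes association and pathway. A model that draws on all domains, with domain-by-domain association tests beneath it, fits both entries without contradiction.

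**What leaves the FDR family open.** Suppose each domain were placed in one tier only. Section 8 would still not say how many SNPs, MRI features or scales are tested, so the family would remain undefined. The overlap blurs the tier label. The missing list of tests leaves the family open.

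**Size of the effect.** The protocol gives no figure to reproduce: the enrolment of 100 has no alpha, power or effect size attached. The following are assumptions: a true correlation of 0.30, full data on all 100 patients, independent tests, FDR level 0.05, and a Fisher-z test standing in for the logistic model.

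- Shift of the test statistic for a real predictor: atanh(0.30) × √(100 − 3) = 0.3095 × 9.849 = 3.05.
- Threshold for the smallest p-value among m tests under Benjamini-Hochberg: 0.05/m.

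| m | Threshold | Power at that threshold |
|---|---|---|
| 10 | 0.005 | 59.5% |
| 15 | 0.0033 | 54.5% |
| 30 | 0.0017 | 46.2% |
| 100 | 0.0005 | 33.3% |

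A lone p = 0.003 therefore passes among 15 tests and fails among 30. Benjamini-Hochberg, however, relaxes its threshold as more real signals appear, so the full procedure was simulated (40,000 sets per row). A family of 15 clinical tests was analysed alone and then pooled with biological tests:

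| Real predictors (clinical / biological) | Pooled size | Clinical power, separate | Clinical power, pooled |
|---|---|---|---|
| 1 / 0 | 30 | 55% | 47% |
| 5 / 0 | 30 | 71% | 61% |
| 1 / 0 | 100 | 55% | 34% |
| 5 / 0 | 100 | 71% | 44% |
| 5 / 5 | 30 | 71.1% | 70.8% |
| 1 / 5 | 30 | 56% | 64% |

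With no real biological predictor, a real clinical predictor that is significant in its own family loses significance on pooling in about 8 to 10% of cases (to 30 tests) or 21 to 27% (to 100). With five real predictors in each family, 1.3% are lost and 1.0% gained. With one clinical and five biological, pooling helps the clinical predictor.

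**Cost of separate families.** When no predictor is real, two independent families each held at 0.05 give at least one false finding with probability 1 − 0.95² = 9.75% (9.5% in the simulation). One pooled family gives about 5%.

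**The case for a change.** The strongest case for a change is that assigning objectives to tiers is the protocol's job. Section 8 is itself headed as the statistical analysis plan, and it separates neither prediction from association nor one family from another. Any later plan would have to choose between two protocol entries. The power figures reproduce, and under some assumptions the family chosen does alter which predictors are declared significant.

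Part of this stands. The overlap is in the text, and one sentence relating the two entries would make the protocol clearer. The heading of Section 8 weakens the appeal to an unseen plan, but does not show that no fuller plan exists.

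The rest does not carry. The large losses arise only when every pooled biological test is null, which runs against the study's own premise in Section 1 that biological variables may contribute to variation in response. The obvious remedy also has defects. Separate correction of a primary clinical and functional family and a biological family fits only if the biological domains are made secondary. If they stay primary, it splits the primary tier in two and nearly doubles the chance of a false finding under the global null. Making them secondary removes declared domains from the main objective, which is more than a change of wording. Optimism in unpenalised prediction models and the absence of function from the baseline list in Section 7 are separate matters and lend no weight here.

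**Conclusion.** The duplication is an editorial ambiguity that analysts can resolve sensibly, and it calls for no change to the plan. The study is observational, single-arm and exploratory, with no stated alpha, power or confirmatory hypothesis, so there is no single pass-or-fail result for a tier label to reverse. Relabelling an entry would alter no estimate, interval or model. The definition of the FDR family and the validation of the models are commonly left to an analysis plan, and one fixed before outcome analysis would settle both. That the tier could be chosen after the data are seen is true of this document as written, but is not shown for the study.

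The choice between pooled and separate families is a trade-off. In the cases examined, pooling 15 clinical tests with 15 biological ones moves clinical power by anything from a loss of about 10 percentage points to a gain of about 9. Pooling to 100 tests with no real biological predictor costs 21 to 27 points. Separate families raise the global-null chance of a false finding from about 5% to about 9.5%. All these figures rest on assumed predictor counts, a correlation of 0.30, independent tests and complete data on 100 patients, none of which the protocol gives except the enrolment figure.

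### Does a single-arm cohort without a comparator overreach when it sets out to evaluate effectiveness?

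*Protocol*

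**What the plan says.** The word at issue appears in two places in the Protocol. Section 2 lists as its first secondary objective "To evaluate the effectiveness and safety of esketamine in a real-world clinical setting". The closing sentence of Section 1 says that "this study aims to deepen understanding of real-world predictors of esketamine effectiveness and safety".

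Section 3 classes the study as observational, gives the design as "Prospective, longitudinal, single-arm (case-only", the duration as "From enrollment to 12 months of treatment" and the size as "Estimated Enrollment: 100". No concurrent or historical control, external cohort, reference response rate or performance threshold is named.

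Two secondary outcomes in Section 6 serve the objective: "Changes in depressive symptoms over time" and "Safety and tolerability (adverse events monitoring". The matching analysis in Section 8 is "Longitudinal analysis (mixed-effects models) for symptom trajectories and functioning". The primary objective and primary outcome are worded in terms of predictors of clinical response. The third secondary objective and the last group of outcomes in Section 6 are worded in terms of association with response.

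**The concern.** Effectiveness can be read causally, as the improvement that esketamine brings about compared with what would have happened without it. A single-arm cohort holds no information on the second half of that contrast. Natural course, regression to the mean, concomitant care and selective retention to 12 months would all appear in the same trajectory as any drug effect.

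The phrase in Section 1 raises a parallel issue. A factor associated with response among treated patients may be prognostic, or it may modify the drug's effect, and treated patients alone cannot show which.

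If the Protocol committed the study to a causal reading, mean improvement could be reported as the drug's effect and a prognostic marker as a predictor of benefit from esketamine. An objective that its own design cannot answer would be a genuine fault.

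**Working it through.** **1. Is there a figure to reproduce?** No. The Protocol gives no response rate, standard deviation, significance level, power, margin or benchmark. The only usable number is n = 100 (Section 3). Every rate below is an assumption.

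**2. What one arm cannot show: effectiveness.** Assume 50 of 100 patients respond.

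- The Wilson 95% interval is 0.404 to 0.596, and the exact interval is 0.398 to 0.602.
- Drug contribution = response on drug minus response off drug. With assumed off-drug rates of 20%, 35% and 50%, this is 50 − 20 = 30, 50 − 35 = 15 and 50 − 50 = 0 points.
- The observed data are the same in all three cases. A larger n narrows the interval but not this range.

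**3. What one arm cannot show: a pre-post test.** Suppose the drug has no effect, patients enter k SD above their long-run mean, and the scale has reliability r. The standardised change from regression to the mean is d = (1 − r)k / √(2(1 − r)). The chance of a significant two-sided 5% test with complete pairs is about Φ(d√n − 1.96).

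- k = 1, r = 0.5: d = 0.50, probability Φ(5.0 − 1.96) ≈ 1.00.
- k = 1, r = 0.8: d = 0.32, probability about 0.89.

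**4. What one arm cannot show: predictors.** Assume 60% response on drug with a factor and 35% without it. The odds ratio is (0.60/0.40)/(0.35/0.65) = 2.79. Two off-drug scenarios fit equally well:

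| Off-drug response (with / without factor) | Drug odds ratio with factor | Drug odds ratio without factor | Reading on the odds scale |
|---|---|---|---|
| 41% / 20% | 1.5/0.696 = 2.15 | 0.538/0.25 = 2.15 | purely prognostic |
| 20% / 20% | 1.5/0.25 = 6.0 | 0.538/0.25 = 2.15 | effect modifier |

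On the risk scale even the first row is not neutral: 60 − 41 = 19 points against 35 − 20 = 15.

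**5. Does the plan rely on any of this?** The steps above are correct. They would also apply unchanged to any single-arm study of 100 patients. The question is whether this Protocol draws an inference that they forbid. The parts line up as follows.

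| Element | Where | What it commits the study to |
|---|---|---|
| Aim | Section 2 | Evaluate effectiveness and safety under routine care |
| Design | Section 3 | Observational, one arm, declared as such |
| Outcome | Section 6 | Symptom change over time; adverse events |
| Analysis | Section 8 | Mixed-effects trajectories |
| Decision rule | none | No hypothesis of efficacy, threshold or reference value |

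Read down the table, the outcome defines the objective: effectiveness here means how symptoms develop in patients treated in practice. One cohort can estimate that. The quantity it cannot estimate, the contrast with no drug, is not named as an outcome or assigned an analysis.

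**6. Does the sentence in Section 1 govern anything?** No. It is background. The operative sections speak of response and of associations with response, and both can be estimated in treated patients. No section claims treatment-specific prediction, so the example in step 4 addresses a claim that the plan does not make.

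**7. What would different wording change?** Nothing in enrolment, the visits at 1, 3, 6 and 12 months, the measurements, the predictor classes, the endpoint or the models. A clarification that predictors are sought among treated patients would be redundant, since the cohort contains no others.

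**The case for a change.** The strongest case for the concern is that the objective is Protocol text and stands whatever an SAP adds. The reference to real-world practice qualifies the setting and not the inference. No sentence says that effectiveness means uncontrolled change. Section 9 plans publication, where a reader may take the word causally. No analysis within this one cohort can supply the missing contrast, and declaring the design does not in itself qualify the objective.

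Part of this stands. The inferential limit is real, the Protocol does not spell it out, and any report of the results must respect it. The rest does not make a fault. An objective is read together with the design, outcome and analysis attached to it, and here all three are descriptive. Real-world effectiveness is common usage in cohorts of this kind. A statement of interpretive limits, or an external benchmark if one were wanted, may reasonably sit in an SAP, which is not at hand. The harm described is a conjecture about later reporting, not a consequence of following the plan.

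**Conclusion.** The concern does not hold. Nothing in the Protocol is stated wrongly or contradicted on this point. A legitimate and openly declared single-arm design is paired with descriptive outcomes and a trajectory analysis, without any causal claim, efficacy hypothesis or success criterion. Followed as written, the plan gives the same sound descriptive results whichever word is used, so the effect on the study's numbers is nil. The spread of 30, 15 or 0 points and the odds ratios above rest on assumed response rates. They show what no single-arm cohort can show, not an error in this one. What is left is a preference about one word.

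This conclusion rests on reading the first secondary objective through the outcomes and analysis listed for it. It would change if the Protocol set a test of efficacy, a threshold for success or a claim of treatment-specific prediction, and it does none of these.

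### Does one weekly dose range, printed beside a twice-weekly and then a weekly schedule, leave the treatment undefined?

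*Protocol*

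**What the plan says.** The treatment is described only in Section 5 (Intervention (Observed Treatment)) of the protocol. The lead line reads "Esketamine nasal spray, administered in accordance with the approved product label". Two sub-bullets follow. The first gives the amount: "Dosage ranging from 28 mg to 84 mg per week". The second gives the frequency: "Twice-weekly administration during the first month", "followed by weekly maintenance".

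Section 3 describes an observational, single-arm study in routine outpatient practice, running "From enrollment to 12 months of treatment". Section 2 lists among the secondary objectives "To evaluate the effectiveness and safety of esketamine in a real-world clinical setting". The protocol gives no dose per administration and no range specific to either phase, and it does not reproduce the label's contents.

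**The concern.** One range covers two phases whose frequency differs by a factor of two. If the weekly total is held to the same limits throughout, the limits per administration must double when the frequency halves. The protocol neither states nor explains that. A reader may therefore suspect that a per-administration range was given a weekly unit by mistake.

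Two things would be at stake. Section 5 is the only account of the treatment whose effectiveness and safety are to be evaluated, so an unclear unit would blur what was studied. The unclear period is also the one that ends at the first follow-up, at 1 month (Section 7). If an analysis classified patients by planned first-month dose, a two-fold misreading would matter.

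**Working it through.** There is no derived figure to reproduce, because the range is stated rather than calculated. The check is to work out both readings and then look for any part of the plan that uses the result.

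**Inputs (all from Section 5)**
- Range: 28 to 84 mg, with the printed unit of mg per week.
- Administrations per week: 2 in the first month, 1 afterwards.

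**Formulas**
- Amount per administration = weekly total / administrations per week.
- Weekly total = amount per administration × administrations per week.

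**Results**

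| Reading | Phase | Per administration | Weekly total |
|---|---|---|---|
| Weekly total, as printed | First month | 28/2 to 84/2 = 14 to 42 mg | 28 to 84 mg |
| Weekly total, as printed | Maintenance | 28/1 to 84/1 = 28 to 84 mg | 28 to 84 mg |
| Per administration | First month | 28 to 84 mg | 2×28 to 2×84 = 56 to 168 mg |
| Per administration | Maintenance | 28 to 84 mg | 28 to 84 mg |

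**Are the two bullets compatible?** Yes. Under the printed unit both can hold at once. A constant amount per administration is possible too: it must lie in 14 to 42 mg for the first month and in 28 to 84 mg for maintenance, which leaves 28 to 42 mg. This shows only that the lines do not contradict each other. It says nothing about which regimen is intended or appropriate.

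**How large is the ambiguity?** In the first month the readings differ by a factor of 56/28 = 168/84 = 2. In maintenance they are identical.

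**Does anything use the range?**
- Section 2 groups the candidate predictors as clinical, biological, psychophysical and functional. Dose is not named.
- Section 6 defines outcomes by symptom scales, functioning, adverse events and associations with genetic, imaging and psychophysical measures. None is defined by dose.
- Section 8 names descriptive statistics, logistic regression and machine learning for response, mixed-effects models for trajectories, and correction for multiplicity. No dose term, exposure variable or dose-based analysis set appears.
- Section 3 gives "Estimated Enrollment: 100" with no calculation that rests on dose.
- The study assigns no dose: treatment is "administered in accordance with the approved product label".

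No stated quantity in the plan changes between the two readings.

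**The case for a change.** The strongest argument for asking for a change is that a protocol which prints its own figures should print them so that they can be read without guessing. Citing the label does not settle the unit for someone holding only this document. The literal reading also has an odd feature, since both limits per administration double at the change of phase and the text does not say so. A clarification would be a small change of wording.

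Part of this stands. The description could be plainer, and the amount and schedule lines would read better if they said how the range applies in each phase. But the unit is not missing: it is printed as a weekly one. Nothing in the protocol refers to an amount per session, so the competing reading requires replacing a printed unit with one the text does not contain. Any firmer suspicion would have to come from the label's contents, which are not in the document.

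The possible use of dose as a covariate, or in a 1-month summary by dose, is hypothetical because the protocol names neither. If an analyst did add dose, the values would sensibly be those actually given to each patient. They would not be read off the range in Section 5.

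**Conclusion.** The observation is accurate, but it does not amount to a fault in the plan. Section 5 does not say how one weekly range applies to two frequencies. As written, the two lines are arithmetically compatible. The most that can be said is that the first-month weekly limits would be 56 to 168 mg instead of 28 to 84 mg if the printed unit were set aside, with no difference afterwards.

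No outcome, analysis, enrolment figure or assigned treatment depends on the answer, so amending the wording would change no result or conclusion. It is an editorial point. If Section 5 is revised for another reason, the amount and schedule lines should be reconciled with each other and with the label the protocol cites. No view is taken here on which dose or reading is right.

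This rests on two assumptions: that prescribing clinicians follow the label, as the protocol says, and that any later analysis of exposure would use doses actually given. A statistical analysis plan may exist that was not available. If it defined groups or analysis sets by planned weekly dose, the unit would need settling there.

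### Functioning is first assessed at month 1, so the plan has no pre-treatment value for functional predictors or for change in functioning

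*Protocol*

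**What the plan says.** Section 2 gives the primary objective as: "To identify predictive factors (clinical, biological, psychophysical, and functional) of clinical response to esketamine". A secondary objective is "To explore changes in psychosocial and occupational functioning over time". Section 6 lists "Changes in social and occupational functioning" as a secondary outcome, and Section 8 plans "Longitudinal analysis (mixed-effects models) for symptom trajectories and functioning".

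Section 7 fixes what is collected and when. At baseline it lists "Clinical, demographic, neuroimaging, genetic, psychophysical assessments". The follow-ups are "At 1, 3, 6 and 12 months" and have three items: clinical scales, "Functional assessments" and safety monitoring. Nothing else in the protocol schedules a functional measure before treatment. The only outcome text that mentions a baseline measurement concerns response, "measured using standard clinical scales (e.g., MADRS) at baseline and regular follow-ups", not functioning.

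**The concern.** A predictor of response has to be measured before the treatment can act on it. On the Section 7 schedule, functioning is first recorded at month 1, when the more intensive first month of treatment is complete. Section 1 itself describes the drug's antidepressant effect as rapid, so month-1 functioning may already carry part of the response it is meant to predict.

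Two things are at stake:

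- **Primary objective.** One of its four predictor classes cannot be tested with a pre-treatment value. An analyst who used the earliest available value would be entering a post-treatment variable.
- **Change in functioning.** Change can be estimated only from month 1. Whatever happens in the first month is unseen, and a patient lost before the month-1 visit contributes no functional value at all.

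**Working it through.** The protocol gives no figure to reproduce here. The main check sets the objectives beside the schedule.

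**Objectives against schedule**

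| Predictor class (Section 2, primary) | Baseline item (Section 7) |
|---|---|
| Clinical | Clinical |
| Biological | Genetic, neuroimaging |
| Psychophysical | Psychophysical |
| Functional | None |

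Functional measurements as scheduled: 0 before treatment and 4 after it starts (months 1, 3, 6 and 12).

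**Could *clinical* at baseline include functioning?** The protocol separates the two terms twice. The primary objective lists them as different classes, and the Section 7 follow-up list gives them as different items. The text does not support reading one inside the other.

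**Exposure before the first functional value.** Section 5 describes two administrations a week in the first month. Taking a month as 4 weeks, 4 x 2 = 8 administrations.

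**Share of change still visible.** Let f be the fraction of the 12-month functional change that occurs by month 1. The protocol gives no value, so f is assumed. The visible share is 1 - f:

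- f = 0.3: 0.7
- f = 0.5: 0.5
- f = 0.7: 0.3

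**Using month-1 functioning as a predictor (illustration).** Only n = 100 comes from the protocol. The assumptions are:

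- Baseline functioning B has SD 1 and is unrelated to response.
- Early improvement has SD 1 and moves month-1 functioning by b, so month-1 functioning is F = B + b x early improvement.
- Early improvement correlates r with improvement at month 3.
- Response is the better half at month 3, and the groups are compared by a two-sided 5% test.

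A median split of a standard normal variable separates the group means by 2 x 0.798 = 1.596 SD. The expected difference in F is therefore 1.596 x b x r. Its standard error, with 50 per group, is sqrt(1 + b²) x 2/sqrt(100). The expected test statistic is z = 7.98 x b x r / sqrt(1 + b²), and the chance of a significant result is P(|Z + z| > 1.96).

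| b | r | z | Flagged as predictor |
|---|---|---|---|
| 0.3 | 0.6 | 7.98 x 0.18 / 1.044 = 1.38 | 28% |
| 0.5 | 0.6 | 7.98 x 0.30 / 1.118 = 2.14 | 57% |
| 0.3 | 0.3 | 7.98 x 0.09 / 1.044 = 0.69 | 11% |
| 0.5 | 0.3 | 7.98 x 0.15 / 1.118 = 1.07 | 19% |
| 0.1 | 0.3 | 7.98 x 0.03 / 1.005 = 0.24 | 6% |

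Simulating 10,000 studies per row agreed to within one percentage point. True baseline functioning was flagged in about 5% throughout. With 30% responders instead of 50%, the first two rows fall to about 25% and 52%.

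**The case against.** The strongest reply is that this is a slip in a one-line list. The protocol's labels are not strictly exclusive: Section 2 places psychophysical tasks under biological pathways in one objective and beside biological factors in another. *Clinical assessments* at baseline is also a looser term than the *clinical scales* at follow-up, and the official title mentions life functioning. The sponsor may well intend to measure functioning at baseline. That is plausible, but sites work from Section 7, which does not ask for it. An oversight needs the same correction as a deliberate choice.

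Second, neither the secondary objective nor the outcome says that change is measured from pre-treatment, and four follow-up values are enough for a mixed model. This stands in part: change from month 1 to month 12 remains estimable, so that outcome is weakened, not lost. Section 3, however, runs the study from enrolment, and change that begins after the first month of treatment is not what a reader would take the outcome to mean.

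Third, the spurious-association rates rest on inputs that are not in the protocol, and nothing in it says month-1 functioning will be used as a predictor. This also stands. The rates shrink towards 5% when the coupling is weak, and they describe what would follow from a substitution the schedule invites, not one the protocol plans. The protocol also sets no time point for response; month 3 is assumed. The finding does not depend on these rates.

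The gap cannot be left to a separate analysis plan. Section 7 sets the data collection, and a value that was never collected cannot be supplied later.

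**Conclusion.** The concern holds. The schedule in Section 7 contradicts the objectives in Section 2: one of four primary-objective predictor classes has no pre-treatment measurement, and change in functioning can be followed only from month 1. Both statements come directly from the text and need no assumption. The other three predictor classes are unaffected.

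The sizes are conditional. The visible share of functional change is 70% to 30% if 30% to 70% of it occurs by month 1. The spurious-association rate is 28% to 57% for coupling of 0.3 to 0.5 SD with correlation 0.6, 11% to 19% with correlation 0.3, and close to 5% when coupling is weaker still.

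This must be fixed before enrolment, because the baseline is lost for good in every patient treated without it.

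**What to change.** Add functional assessments to the Baseline line of Section 7, using the same instruments as at follow-up and completed before the first esketamine administration. Name those instruments, since the protocol names none. Use the baseline value as the functional predictor. In the mixed model for functioning, use it as the time-zero observation or as a baseline covariate; the analysis plan can settle which. State that functional values from month 1 onward are not candidate predictors of response.

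If baseline functioning will not be collected, the alternative is to remove functional factors from the primary objective and describe the functioning outcome as change from month 1.

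The first option costs one line of protocol text and one extra administration, at an existing baseline assessment, of instruments already due at four later visits. The added patient time should be small, though it cannot be sized until the instruments are named. If enrolment has already begun, report how many patients lack the baseline value.
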